#### **6.4.1.2. Duration of MRD Negativity**

If data permits, DOMRD will be analyzed using Kaplan-Meier method in participants who have achieved negative MRD and confirmed sCR/CR. DOMRD is defined, for participants with negative MRD, as the time from first documentation of negative MRD to the date of first documentation of relapse or death due to any cause. Relapse is defined as any one or more of the following criteria:

- Loss of MRD negative state (evidence of clonal plasma cells on NGF or NGS, or positive imaging study for recurrence of myeloma);
- Reappearance of serum or urine M-protein by immunofixation or electrophoresis;
- Development of  $\geq 5\%$  clonal plasma cells in the bone marrow;
- Appearance of any other sign of progression.

The following exploratory endpoints analyses may be performed. The results may be presented separately from the main CSR.

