When PD (clinical or biochemical) is suspected, applicable tests (eg, SPEP, SIFE, UPEP, UIFE, serum FLC tests) should be repeated for confirmation prior to initiation of new anticancer therapy.

Note that if a participant had measurable serum or urine M-protein (M-spike) at baseline, unless the band is due to/confounded by the presence of daratumumab or other therapeutic mAb, PD cannot be defined by increases in serum FLC alone. Serum FLC levels should only be used for response assessment when both the serum and urine M component levels are deemed not measurable or uninterpretable. Furthermore, careful attention should be given to new positive immunofixation results appearing in participants who have achieved a CR, when the isotype is different. This may represent oligoclonal immune reconstitution and should not be confused with relapse; these bands typically disappear over time.

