8.6.1. Bone Marrow Aspirate for Minimal Residual Disease (MRD)

A BMA sample will be taken at the time points specified in the individual [sub-study protocol](#) SoAs. NGS of the pre-dose sample identifies rearranged immune receptors (eg, IgH, IgK, and IgL receptor gene sequences), as well as select translocation sequences. This unique immunoglobulin receptor repertoire defines the participant-specific dominant malignant plasma cell clone (the index clone) and is used as a reference that is compared to subsequent samples collected after initiation of treatment. BMA samples will be used to determine the MRD negativity rate with a threshold of **0.01** whenever a BMA/BMB sample is taken for disease response evaluation.

Screening Sample: A BMA sample collected at screening will be used for identification of the dominant (index) malignant clone. If the central laboratory is unable to identify the dominant (index) malignant clone with the screening sample, or if the participant does not have a BMA collected at screening, the site can submit an archival BMA sample. If an archival sample is not available, but the participant has a test result from a previous Adaptive Biotechnologies clonoSEQ® MRD assay performed at their Seattle, WA (US) laboratory that identified the index multiple myeloma clone, and the result is retrievable and useable in this study, the sponsor may give approval to use this result instead of submitting an alternative BMA sample.

If neither of these two options are available, the site can submit an alternative BMA sample collected at screening. Acceptable alternative or archival sample types include:

- Cells pellet/suspension from BMA, minimum 1 million cells, or
- 1 million frozen BMBCs dry cell pellet or cell suspension collected from fresh BMA, or
- BMA smear slides or touch prep slides, 3-5 slides total, or
- Re-cut slides from bone marrow clot tissue block, minimum 5 slides, 8 microns thick, or
- Re-cut scrolls from a bone marrow clot tissue block, minimum 8 scrolls, 5 microns thick, or
- Genomic DNA (gDNA) isolated from bone marrow aspirate

On-Treatment sample: A freshly collected BMA sample for MRD determination is required at various times during treatment (ie, after C0D1). If the central laboratory is unable to determine MRD status with the on-treatment sample that was submitted, the sponsor may request an alternative sample type from the same collection.

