#### 6.2.8. Minimal Residual Disease Negativity Rate

MRD negativity rate is defined as the proportion of participants with CR or better by investigator and negative MRD (assessed by central lab) per IMWG sequencing criteria at any time from the date of first dose until the first documentation of confirmed PD, death or start of new anticancer therapy, whichever occurs first. The rules for PD confirmation are described in [Table 2](#).

MRD negativity will be defined by two thresholds, CCI.

The MRD negativity rate will be calculated along with the 2-sided 95% CI using the Clopper-Pearson method as follows:

- MRD negative with confirmed sCR/CR based on the Safety Analysis Set;

- MRD negative based on the subset who achieved confirmed sCR/CR in the Safety Analysis Set;
- MRD negative based on the subset of MRD evaluable patients (achieve sCR/CR and have at least one MRD assessment).

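### Sub-study B duration of MRD negativity (exploratory): one unconfirmed immunofixation result counts as relapse, and the clock can start before the complete response needed to enter the analysis

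*SAP*

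**What the plan says.** The Sub-study B SAP lists DOMRD as an exploratory efficacy endpoint (3.3.1) and defines it in 6.4.1.2. The analysis is conditional: "If data permits, DOMRD will be analyzed using Kaplan-Meier method". The set is "participants who have achieved negative MRD and confirmed sCR/CR", and the duration is defined "as the time from first documentation of negative MRD to the date of first documentation of relapse or death due to any cause".

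Relapse is any one of four criteria. The first begins "Loss of MRD negative state (evidence of clonal plasma cells on NGF or NGS" and also allows a positive imaging study. The second is "Reappearance of serum or urine M-protein by immunofixation or electrophoresis". The third is a clonal marrow plasma cell percentage of 5% or more, and the fourth is any other sign of progression. The section states no confirmation rule, isotype rule or MRD threshold.

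For the MRD negativity rate, 6.2.8 says that "MRD negativity will be defined by two thresholds"; the values are redacted.

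Protocol 8.1.1 discusses new positive immunofixation results of a different isotype in participants who have reached CR. It says: "This may represent oligoclonal immune reconstitution and should not be confused with relapse; these bands typically disappear over time". Appendix 11, footnote b, repeats the caution.

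**The concern.** A duration endpoint needs an event that reliably marks the end of the state and a start date that fits the way participants enter the set. Section 6.4.1.2 is loose on both.

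**Event.** Immunofixation is very sensitive and is repeated often during CR. If one positive result of any isotype ends DOMRD, a transient band that the protocol tells investigators not to call relapse can be scored as one. In the same SAP, PFS, DOR and DOCR end only at progression that is later confirmed.

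**Start date.** If the first negative MRD precedes CR, the time between them enters the Kaplan-Meier curve only for participants who went on to reach confirmed CR. Those who died or had confirmed progression first are not in the set.

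At stake is whether the curve describes how long MRD negativity lasts. The cohort at the recommended dose is at most 20, including 6 from escalation (SAP 5.1.1.2), and DOMRD uses a subset of it, so a few misclassified events would visibly move the curve.

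**Working it through.** The plan gives no figure for DOMRD, so there is none to reproduce. The check compares the relevant sections, followed by an illustration on assumed inputs.

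**1. Does another rule confirm the immunofixation event?** The confirmation rule in SAP 6.2.1 and its Table 2 is written for PD. PFS, DOR and DOCR (6.2.3 to 6.2.5) refer to it explicitly. Section 6.4.1.2 uses the word relapse, refers to no table, and dates the event at first documentation. Protocol 8.1 and Appendix 11 require two consecutive assessments for response categories and PD, but do not mention DOMRD relapse. As written, one result is enough.

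**2. How often is the test run?** Protocol 8.1.1 requires serum immunofixation when electrophoresis shows no measurable protein, so it recurs while a participant stays in CR.

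**3. Illustration of the event problem.** Inputs:
- Tests per year: 52 weeks / 4 = 13. This assumes four-weekly testing, in line with the 28-day spacing in SAP 6.2.1.
- False-positive rate per test, f: assumed, 0.5% to 5%. No document gives a value.
- Independence between tests: assumed.

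The chance of at least one false positive in 13 tests is 1 − (1 − f)^13. The chance of two in a row comes from a three-state recursion, with a = last test negative, b = last test a single positive, c = two consecutive positives seen. At each test, a becomes (a + b)(1 − f), b becomes a·f, and c becomes c + b·f.

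For the median, assume exponential times with true median m months. The added monthly hazard is h = −ln(1 − f) / (28/30.4375), and the observed median is ln 2 / (ln 2/m + h). At f = 1% and m = 12, h = 0.0109 and the observed median is 0.6931 / (0.0578 + 0.0109) = 10.1 months.

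| f per test | False relapse in a year, single result | Two consecutive required | Observed median if true 12 months | Observed median if true 24 months |
|---|---|---|---|---|
| 0.5% | 6.3% | 0.03% | 11.0 | 20.2 |
| 1% | 12.2% | 0.12% | 10.1 | 17.4 |
| 2% | 23.1% | 0.47% | 8.7 | 13.6 |
| 5% | 48.7% | 2.8% | 6.1 | 8.2 |

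Oligoclonal bands may persist over several visits, in which case results are correlated and a second sample protects less than the third column suggests. The isotype condition is needed as well.

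**4. Can the first negative MRD precede CR?** Protocol 8.1.2 sends marrow to the central laboratory for MRD when the participant is in suspected or actual CR. Protocol 8.6.1 describes MRD determination "whenever a BMA/BMB sample is taken for disease response evaluation". So a negative result can carry a date before the first documentation of CR. SAP 3.2.1.8, 6.2.8 and 6.4.1.2 each list CR as a condition separate from negative MRD, so negative MRD alone does not fix the start at CR.

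**5. What does selection remove?** SAP 3.2.1 assesses best response only up to confirmed PD, death or new anticancer therapy. A participant who dies or has confirmed PD between negative MRD and CR therefore never qualifies. The interval is free of those two events by construction, though not necessarily of every relapse criterion; a positive MRD could still occur in it.

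**6. Illustration of the start-date problem.** If the gap is g months for everyone, with no event in it, the median from first negative MRD is m + g. With assumed g of 1, 3 or 6 months, a median of 12 months from CR becomes 13, 15 or 18, and 24 becomes 25, 27 or 30.

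**The case against.** **Immunofixation.** Reappearance suggests the return of the protein originally present, so a different isotype would not qualify, and the protocol already carries the caution. DOMRD may also be meant as a more sensitive endpoint than PD. The first argument has force: an investigator following the protocol would avoid some false calls. But 6.4.1.2 is the derivation rule, and neither the isotype condition nor the caution is in it. A sensitive endpoint may reasonably use immunofixation; that does not explain accepting a single result.

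**Start date.** Appendix 11 makes CR part of the sequencing MRD-negative category. Read strictly, the first negative MRD could not precede CR. Section 6.4.1.2 does not say this, and on that reading its separate sCR/CR condition would be largely redundant. What stands is that the clock can start before CR, not that it always does. Any gap is probably limited mainly to suspected CR.

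**Threshold.** A reader might infer that clonal cells below the negativity threshold count as relapse, so that a sample lying between the two thresholds ends DOMRD on the day it starts. The documents do not support this. The criterion is loss of the MRD-negative state, and a sample still below the threshold in force has not lost it. All that remains is that 6.4.1.2 does not say which threshold applies.

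**Size.** The false-positive rates, gaps and medians above are assumptions. That objection stands in full.

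**Conclusion.** Two parts of the DOMRD definition are wrong as written. The event rule accepts one immunofixation result without an isotype or confirmation condition, contrary to the protocol's own caution; this can shorten DOMRD. The start date does not match the entry conditions, so time before CR that is free of death and confirmed PD by selection can be included; this can lengthen it.

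The documents do not allow either effect to be estimated. A reader might want to conclude that DOMRD is biased in a known direction, but the two effects oppose each other and the net sign and size cannot be determined. Nor can they be assumed to cancel.

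Importance is minor. DOMRD is exploratory and analysed only if data permit, in a subset of a small cohort. SAP 5.1.2.2 states that the expansion part has no decision rule, and no primary or secondary endpoint depends on DOMRD.

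**What to change.** Change three points in section 6.4.1.2 of the Sub-study B SAP:

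1. **Event.** Count only reappearance of the participant's original, same-isotype M-protein, confirmed on a second consecutive sample and dated at the first. This follows the way PD is dated for PFS, DOR and DOCR. An unconfirmed band at data cutoff would not be an event.
2. **Start date.** Start DOMRD at the later of the first negative MRD and the first documentation of sCR/CR that is subsequently confirmed.
3. **Clarification only.** State that loss of MRD negativity is judged at the same threshold that defined negativity.

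The cost is a few sentences in one exploratory section, with no new samples or assays. The sponsor should check that the isotype of each positive immunofixation is available in the database. Some durations will shorten under the second change, and some early events will drop out under the first.

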### **6.4.2. Biomarker Analysis**

Biomarker data including DNA, RNA, protein, metabolites, or defined cell types resulting from analyses of peripheral blood, and/or BM biospecimens will be assessed based on the Biomarker Set.

Exploratory biomarker endpoints will not be reported in CSR, but in a separate biomarker report.

### **6.4.3. Patient-Reported Outcomes**

The following PRO analyses will be performed to support the CSR development. Analyses of the PRO endpoints will be based on the PRO Analysis Set.

## **Completion Status**

The number and percentage of participants who completed the PRO at each time point will be summarized, as will the reasons for non-completion. A PRO is considered completed if at least one item was answered by the participant.

## **EORTC QLQ-CIPN20**

This questionnaire contains 20 questions which can be grouped into a sensory subscale (9 items), motor subscale (8 items) and autonomic subscale (3 items). The analysis of the QLQ-CIPN20 subscales will consist of descriptive statistics based on observed values and change from baseline values. Number and percent will be summarized for the item-level responses at each visit.

### **6.5. Subset Analyses**

All the subset analyses will be exploratory and descriptive; no adjustment for multiplicity will be performed. Analyses will only be performed if there is sufficient sample size. The determination of whether or not there is sufficient sample size will be defined after enrollment is complete and prior to database lock. As a general rule, analyses of ORR will only be performed if there are  $\geq 10$  participants overall within the defined subset. Deviations from these analyses will be described in the clinical study report.

The following subset analyses will be performed for ORR for the RP2D cohort based on the Safety Analysis Set:

- Baseline cytogenetics (high vs standard risk);
- Baseline extramedullary disease (yes vs no);
- Prior stem cell transplant (yes vs no);
- Disease stage (1-2 vs 3);
- Number of prior therapies ( $\leq 4$ ,  $>4$ );
- Type of myeloma (IgG vs non-IgG vs light chain only);
- Age ( $<65$  vs  $\geq 65$ ;  $<75$  vs  $\geq 75$ ).

ORR in subsets will be presented in a forest plot. Other subset analyses will be performed as well if deemed clinical meaningful and feasible (sufficient sample size).

### **6.6. Baseline and Other Summaries and Analyses**

#### **6.6.1. Baseline Summaries**

See [Section 6.5.1 of the master SAP](#) for baseline summaries.

### 6.6.2. Study Conduct and Participant Disposition

See [Section 6.5.2 of the master SAP](#) for summaries of study conduct and participant disposition.

### 6.6.3. Study Intervention Exposure

Exposure will be summarized based on the Safety Analysis Set.

#### 6.6.3.1. Exposure to Elranatamab

Elranatamab is administered as a subcutaneous injection based on the dosing schedule as described in Table 5.

**Table 5. Study Intervention Dose Levels and Administration**

Dose Levels (DL)	Elranatamab (SC)	Lenalidomide (PO)	Dexamethasone (PO)
1 (starting dose level)	2 step-up Priming Doses: 12 mg C0D1 /32 mg C0D4  Full Dose: 44 mg at C0D8, then 44 mg QW starting on C1D1 (28-day cycle)	15 mg QD starting on C1D1 for 21 days (28-day cycle)	20 mg QW, starting on C1D1 (28-day cycle) Only for C1 and C2
2a	2 step-up Priming Doses: 12 mg C0D1 /32 mg C0D4  Full Dose: 44 mg at C0D8, then 44 mg QW starting on C1D1 (28-day cycle)	25 mg QD starting on C1D1 for 21 days (28-day cycle)	20 mg QW, starting on C1D1 (28-day cycle) Only for C1 and C2
2b	2 step-up Priming Doses: 12 mg C0D1 /32 mg C0D4  Full Dose: 76 mg at C0D8, then 76 mg QW starting on C1D1 (28-day cycle)	15 mg QD starting on C1D1 for 21 days (28-day cycle)	20 mg QW, starting on C1D1 (28-day cycle) Only for C1 and C2
3	2 step-up Priming Doses: 12 mg C0D1 /32 mg C0D4  Full Dose: 76 mg at C0D8, then 76 mg QW starting on C1D1 (28-day cycle)	25 mg QD starting on C1D1 for 21 days (28-day cycle)	20 mg QW, starting on C1D1 (28-day cycle) Only for C1 and C2
De-escalation levels			
(-1) (one dose level below DL1)	2 step-up Priming Doses: 12 mg C0D1 /32 mg C0D4  Full Dose: 44 mg at C0D8, then 44 mg QW starting on C1D1 (28-day cycle)	10 mg QD starting on C1D1 for 21 days (28-day cycle)	20 mg QW, starting on C1D1 (28-day cycle) Only for C1 and C2
(-2) (de-escalate from DL2b if DL2b is not tolerable)	2 step-up Priming Doses: 12 mg C0D1 /32 mg C0D4  Full Dose: 76 mg at C0D8, then 76 mg QW starting on C1D1 (28-day cycle)	10 mg QD starting on C1D1 for 21 days (28-day cycle)	20 mg QW, starting on C1D1 (28-day cycle) Only for C1 and C2

090177e1993a4a6d\Approved\Approved On: 31-Jan-2022 16:54 (GMT)

For dose escalation and dose expansion, a priming dose regimen will be applied within the first cycle of elranatamab treatment (C0), composed of 2 step-up priming doses (12 mg at C0D1 and 32 mg at C0D4), followed by the first full dose of elranatamab at C0D8 (44 mg or 76 mg), according to the dose-escalation design described in [Figure 1](#). Both premedication and the priming dose regimen will mitigate the risk of CRS during C0.

A minimum of 2 days should be maintained between the 2 step-up doses (C0D1 and C0D4) and a minimum of 3 days between C0D4 and the first full dose (C0D8); a minimum of 6 days is required between doses thereafter.

The summary of treatment exposure to elranatamab will include the following information:

- Treatment duration (weeks);
- Number of cycles started per participant (mean, median, min, max);
- Number and percent of participants starting a cycle (any cycle, cycle 0, 1, 2, 3, 4, 5, 6, 7, 8, 9, 10, 11, >=12 cycles);
- Total cumulative dose (mg);
- Overall dose intensity (mg/week);
- Overall relative dose (%);
- Overall relative dose intensity (%);
- Number and percent of participants after 6 cycles who switched from QW to Q2W;
- Number and percent of participants, among those switching from QW to Q2W, who switched back to QW.

The treatment duration of elranatamab (in weeks) during the study for a participant is defined as:

- Treatment duration (weeks) = (last dose date – first dose date + 1)/7

Planned treatment duration and intended treatment duration are needed to calculate dose intensity (DI) and relative dose intensity (RDI). It is defined as follows:

- Planned treatment duration (weeks) = 2(2 week for Cycle 0) + number of cycles started × 4 - (number of weeks in the last cycle after permanent treatment discontinuation or data cutoff for those on-treatment).
- Intended treatment duration (weeks) = (last zero/non-zero dose date – first dose date)/7 + 1 if on QW or 2 if on Q2W

**Note:** If C0D4 is the last visit and dose is given at this visit, duration is 1 week.

The planned dose for a given cycle is defined as:

- Cycle 0:
  - Planned dose (mg/cycle) = Planned priming dose(s) per protocol during C0
- After Cycle 0:
  - If the participant is on QW dosing schedule for the cycle:  
Planned dose (mg/cycle) = Full dose × 4
  - If the participant is on Q2W dosing schedule for the cycle:  
Planned dose (mg/cycle) = Full dose × 2

**Note:** Full dose=44 or 76 mg depends on DLs. For the last cycle, subtract planned doses after a participant permanently discontinues treatment or data cutoff for those on-treatment.

The total planned dose is the sum of the total planned dose across all cycles.

The total cumulative dose (mg) of elranatamab is the sum of the actual doses that the participant received during the study; the cumulative dose (mg) of elranatamab per cycle is the sum of the actual doses that the participant received within that cycle (ie, total dose administered [mg]).

The overall DI, relative dose (RD), and the RDI will be calculated for each participant across all cycles and also for each individual cycle:

- Overall DI (mg/week) = Total cumulative dose (mg)/Intended treatment duration (weeks);
- Overall planned DI (mg/week) = Total planned dose (mg)/ Planned treatment duration (weeks);
- Cycle DI (mg/week) = Cumulative dose for a given cycle (mg)/actual cycle duration (in weeks);
- Cycle Planned DI (mg/week) = Total planned dose for a given cycle (mg)/4 weeks.

The RD and RDI are defined as follows:

- Cycle RD (%) = Total given dose for a given cycle (mg) /Total planned dose for a given cycle (mg) × 100;
- Overall RD (%) = Total cumulative dose (mg) /Total planned dose (mg) × 100;

- Cycle RDI (%) = Cycle DI (mg/week) /Cycle Planned DI (mg/week) × 100;
- Overall RDI (%) = Overall DI (mg/week) /Overall Planned DI (mg/week) × 100.

Cycle DI and Cycle RDI will be summarized and plotted vs time (weeks).

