### 5.2.5. Definition of Cycle and Cycle Day

Cycle start and end dates are derived per participant. The definition for each cycle is driven by study intervention PF-06863135.

The first cycle of PF-06863135 is 35 days from Cycle 0 Day 1 through Cycle 1 Day 28 (the 1-week period after the priming dose of PF-06863135 on Cycle 0 Day 1, plus 4 weeks of combination study intervention that begins on Cycle 1 Day 1). Starting from Cycle 2, PF-06863135 is administered on Days 1, 8, 15 and 22 of each 28-day cycle. As described in Section 12.5.2 of the protocol, if a participant has received QW dosing for at least 6 cycles and has achieved an IMWG response category of PR or better persisting for at least 2 months, the dosing interval will be changed from QW to Q2W. If the participant subsequently begins to have an increase of disease burden not yet qualifying as PD according to IMWG criteria, dose intervals should return to weekly dosing. If the dose interval is changed, cycles should remain the same length (ie, 4-week cycles). In either dosing scenario, the nominal cycle length is 28 days (except Cycle 1 is 35 days).

- For Cycle X, the actual cycle start date for each participant is the earliest start date of dosing in the Cycle X Day 1 visit CRF exposure page, if the participant received study intervention on that visit (ie, any study drug with dose >0 at that visit).

- For all but the last cycle:
  - Actual cycle stop date is calculated as the start date of the next cycle minus 1 day;
  - Actual cycle duration is calculated from Day 1 of a cycle to the day prior to Day 1 of the next cycle, as follows:
    - Actual Cycle Duration (weeks) = (cycle stop date – cycle start date + 1)/7.

For the last cycle, actual cycle duration is the planned cycle duration and actual cycle stop date is calculated as actual cycle start date + 28 – 1 day.

The cycle day will be calculated as:

$$\text{Cycle day} = \text{Date of the assessment/event} - \text{cycle start date} + 1.$$

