### Dose Escalation Design:

[figure not shown]
Approximately 3-6 DLT-evaluable participants will be treated at each dose level of the combination therapy. If DL1 is tolerated, two cohorts (DL2a and DL2b) will be initiated in parallel and arm allocation for participants follows an alternative allocation scheme. DL2a and DL2b must be considered tolerable before DL3 can be opened. Before moving to the next dose level, the safety data will be evaluated by a dose level review committee once evaluable participants have been followed for a minimum of 42 days after the first dose of elranatamab (14 days from the first elranatamab dose + first 28 days following the first dose of the combination of elranatamab, lenalidomide, and dexamethasone).

Dose escalation/de-escalation decisions will be guided by a BLRM approach to determine the MTD of elranatamab when administered in combination with lenalidomide and dexamethasone. However, other evidence such as safety data beyond DLT window, clinical activity, PK, and pharmacodynamics data will also be evaluated in determining the RP2D. The RP2D will be determined with agreement between the investigators and the Sponsor at the dose level review committee.

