## 5.2. General Methods

Unless otherwise specified, all analyses will be performed for dose escalation and expansion separately and with the cohort of RP2D in dose escalation and expansion combined.

For the dose escalation part of the study, all analyses will be performed by dose level and with all dose levels combined as well.

See [Section 5.2 of the master SAP](#) for the detail of the general statistical methods.

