#### 6.6.3.4. Dose Reductions, Interruptions, and Delays

##### **Dose Reduction**

A dose reduction is defined as a nonzero dose that is less than the planned dose. The planned dose is the same as the prior dose except for elranatamab at C0D4 and C0D8.

For each study treatment, the number and percentage of participants with at least 1 dose reduction as well as a breakdown of dose reductions (1/2/3/ ≥4) will be summarized by dose cohort (dose escalation part) and treatment arm (dose expansion). In addition, the number and percentage of participants with at least 1 dose reduction due to an AE will also be summarized.

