#### Statistical Model

The statistical model for dose-DLT data CCI

The monotherapy RP2D of elranatamab is 76 mg, which was determined in Study C1071001. In this sub-study, the initial dose level of elranatamab will be 44 mg with two step-up priming doses of 12 mg on C0D1 and 32 mg on C0D4 for the first dose. The initial dose level of lenalidomide is 15 mg QD, and the dose level of dexamethasone will remain at 20 mg at all dose levels.

CCI

CCI

[figure not shown]

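### Sub-study B: as worded, the planned Cycle 0 elranatamab dose leaves out the Day 8 full dose, and per-cycle planned dose intensity divides a two-week Cycle 0 by four weeks

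*SAP*

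**What the plan says.** All of this is in the Sub-study B SAP unless stated otherwise.

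- **Schedule.** Table 5 (6.6.3.1) gives elranatamab 12 mg on C0D1 and 32 mg on C0D4 as step-up priming doses. It lists the C0D8 dose separately, as a full dose of 44 or 76 mg. The text below the table says that the step-up doses are "followed by the first full dose of elranatamab at C0D8 (44 mg or 76 mg", according to dose level). Appendix 1 names as priming only "two step-up priming doses of 12 mg on C0D1 and 32 mg on C0D4".
- **Planned dose.** For Cycle 0: "Planned dose (mg/cycle) = Planned priming dose(s) per protocol during C0". After Cycle 0, it is four full doses per weekly cycle or two per two-weekly cycle.
- **Received dose.** Every dose actually given counts, both overall and within each cycle.
- **Cycle 0 length.** The planned-duration formula uses 2 weeks. Section 2.2 agrees: "14 days from the first elranatamab dose + first 28 days following the first dose of the combination".
- **Per-cycle planned dose intensity.** "Cycle Planned DI (mg/week) = Total planned dose for a given cycle (mg)/4 weeks", with no exception for Cycle 0.
- **Reporting.** Overall relative dose (RD) and overall relative dose intensity (RDI) are listed outputs. Cycle dose intensity and Cycle RDI are to be summarised and plotted.

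**The concern.** There are two independent faults.

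First, the C0D8 dose falls between the two planned-dose terms. It is labelled a full dose, so the Cycle 0 term (priming only) does not take it. It is given in Cycle 0, so the full-dose term (after Cycle 0) does not take it either. It is still in the numerator.

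Second, the planned intensity for Cycle 0 is spread over twice the cycle's real length.

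Both push the ratios up. A reader of the exposure tables would see over-delivery where there was exact compliance, and full delivery where a full dose was missed. The effect is largest for participants who stop early. In Cycle 0 it also differs between the 44 mg and 76 mg levels, which Section 5.2 has analysed by dose level, so it would show a difference between levels that is not real.

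**Working it through.** The SAP states no numeric planned dose, RD or RDI, so there is no figure to reproduce. The check applies its formulas to a participant who receives every dose on schedule.

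**Inputs**

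- Priming total: 12 + 32 = 44 mg at every dose level (Table 5).
- Full dose F: 44 mg (levels 1, 2a, −1) or 76 mg (levels 2b, 3, −2), given on C0D8 and weekly from C1D1 (Table 5).
- k: completed weekly cycles after Cycle 0, each with planned dose 4F (6.6.3.1).
- Cycle 0 length: 2 weeks (6.6.3.1). Cross-check from the DLT window in 2.2: 42 − 28 = 14 days.
- Actual Cycle 0 duration for a participant who continues to Cycle 1: from its start to the day before the next cycle starts (master SAP 5.2.5), so 2 weeks on schedule.

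**Step 1: overall RD, full compliance**

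Received = 44 + F + 4Fk. Planned as written = 44 + 4Fk.

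| k | F = 44 mg | F = 76 mg |
|---|---|---|
| 1 | 264/220 = 120.0% | 424/348 = 121.8% |
| 2 | 440/396 = 111.1% | 728/652 = 111.7% |
| 6 | 1144/1100 = 104.0% | 1944/1868 = 104.1% |

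After six weekly plus six two-weekly cycles the ratio is (44 + 37F)/(44 + 36F): 1672/1628 = 102.7% and 2856/2780 = 102.7%.

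**Step 2: one full dose missed**

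Received becomes 44 + 4Fk, which equals the planned dose as written, so overall RD reads 100%. The share of the Table 5 schedule actually delivered is:

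| k | F = 44 mg | F = 76 mg |
|---|---|---|
| 1 | 220/264 = 83.3% | 348/424 = 82.1% |
| 2 | 396/440 = 90.0% | 652/728 = 89.6% |
| 6 | 1100/1144 = 96.2% | 1868/1944 = 96.1% |

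**Step 3: overall RDI**

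On weekly dosing the last dose falls 28k + 7 days after the first. Intended duration is (28k + 7)/7 + 1 = 4k + 2 weeks. If the count of cycles started excludes Cycle 0, planned duration is 2 + 4k weeks. The durations cancel and overall RDI equals the RD values in Step 1.

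If the count includes Cycle 0, planned duration after one cycle is 2 + 2 × 4 = 10 weeks. Overall RDI is then (264/6)/(220/10) = 200% at the 44 mg levels and (424/6)/(348/10) = 203% at the 76 mg levels. The four-week divisor plays no part here, because overall planned intensity already allows 2 weeks for Cycle 0.

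**Step 4: Cycle 0 RDI, participant continues to Cycle 1**

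Received in Cycle 0: 44 + 44 = 88 mg, or 44 + 76 = 120 mg.

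| | F = 44 mg | F = 76 mg |
|---|---|---|
| Divisor error only (C0D8 counted as planned) | (88/2)/(88/4) = 200% | (120/2)/(120/4) = 200% |
| Both errors, as written | (88/2)/(44/4) = 400% | (120/2)/(44/4) = 545% |
| Both corrected | (88/2)/(88/2) = 100% | (120/2)/(120/2) = 100% |

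With C0D8 counted, overall RD is also 100% at every k.

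**The case against.** **Priming could mean the whole Cycle 0 regimen.** The formula defers to the protocol, and the sub-study B protocol is not in the file. The text under Table 5 describes a priming regimen within Cycle 0 loosely enough that C0D8 might belong to it. If so, the first fault is only a wording ambiguity. This cannot be ruled out, but the SAP weighs against it. Table 5 and the dose-spacing rule in 6.6.3.1 both separate the two step-up doses from the full dose on C0D8, and Appendix 1 names only 12 mg and 32 mg as priming. Sub-study A SAP 6.6.3.1 uses the same Cycle 0 formula correctly, because there the full dose starts on C1D1. The dexamethasone plan in Sub-study B SAP 6.6.3.3 does count Cycle 0 Day 8. The dose-reduction rule, "The planned dose is the same as the prior dose except for elranatamab at C0D4 and C0D8", shows that C0D8 has a planned dose of its own, but does not say which planned-dose term holds it. The divisor fault does not depend on this question.

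**The overall RDI figures rest on an assumption.** This stands. The output list counts Cycle 0 among cycles started, so the formula can be read either way (Step 3). Overall RD does not depend on it.

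**The last-cycle rule.** Sub-study B SAP 5.2 sends the reader to master SAP 5.2 "for the detail of the general statistical methods". For the last cycle, master SAP 5.2.5 says "actual cycle stop date is calculated as actual cycle start date + 28 – 1 day". A reader might infer that a participant whose last cycle is Cycle 0 gets a four-week actual duration, which would cancel the divisor error. The documents do not support this. The same sentence first sets actual duration equal to planned duration, which is 2 weeks here, and Cycle dose intensity divides by duration rather than by stop date. The two clauses simply disagree for a two-week Cycle 0. Inheritance is also uncertain: 5.2.5 was written for a one-week Cycle 0, and several of Sub-study B's pointers to the master SAP (6.5.1, 6.5.2, 6.5.4, 6.5.5, 6.6) do not match the section numbers in the master SAP on file.

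**The effect is small.** Largely true. Overall RD is about 104% after six cycles. Cumulative dose, treatment duration and the interruption table (6.6.3.4) are unaffected, so a missed dose is still visible there.

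**Conclusion.** The point holds as a minor defect in exposure definitions.

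- **Planned Cycle 0 dose.** On the better-supported reading, C0D8 is received but never planned. Overall RD under full compliance is overstated by about 20 percentage points after one weekly cycle, 11 after two and 4 after six, and one missed full dose is hidden. This is conditional on the sub-study B protocol not treating C0D8 as a priming dose. Overall RDI takes the same values only if cycles started excludes Cycle 0.
- **Divisor.** The four-week denominator is wrong for Cycle 0 however priming is read. It doubles Cycle 0 RDI for a compliant participant who goes on to Cycle 1, giving 400% or 545% when combined with the omitted dose.

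A reader might infer that safety conclusions or dose selection are compromised. The documents do not support that. Dose recommendations rest on DLT probabilities and wider safety, activity and PK evidence. The hold rules count participants with events, and the primary endpoints are DLTs, adverse events and laboratory abnormalities. None uses RD or RDI. The harm is limited to misleading descriptive summaries of overall RD, overall RDI and Cycle RDI.

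**What to change.** In Sub-study B SAP 6.6.3.1:

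1. Define the planned Cycle 0 elranatamab dose, for the RD and RDI calculations, as all elranatamab doses that Table 5 schedules in Cycle 0, including C0D8. That gives 88 mg at the 44 mg levels and 120 mg at the 76 mg levels. If the protocol already counts C0D8 as priming, say so explicitly in the SAP.
2. Use 2 weeks as the Cycle 0 denominator in Cycle Planned DI and keep 4 weeks for later cycles.
3. State that the number of cycles started in the planned-duration formula excludes Cycle 0.

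In addition, reconcile the two clauses of the last-cycle rule in master SAP 5.2.5 for a two-week Cycle 0, or give Sub-study B its own rule.

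The cost is SAP wording and derivation code. No new data are needed, and the dosing schedule does not change.
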